6.0 PATIENT ELIGIBILITY

6.1 Inclusion Criteria

- 6.1.1 Patients with new diagnoses of non-M3 AML (See study document '2008 WHO Classification of AML') or high-risk MDS, (See study document '2008 WHO Classification and Criteria for MDS') myeloproliferative neoplasms (MPN), or myelofibrosis (MF) (MDS, MPN, or MF showing 10% or more blasts in bone marrow) who:
 - 6.1.1.1 Present for an AML-like treatment that could plausibly produce a complete remission (CR); for example intensive induction chemotherapy, low dose single agent chemotherapy, hypomethylation agent, or a similar therapy
 - 6.1.1.2 Potentially possible to retrieve follow-up records from the collaborating institution or treating primary care physician.
- 6.1.2 Patients with primary refractory or first relapse presenting for salvage chemotherapy will be allowed
- 6.1.3 Patients of ≥ 18 years of age and are being treated by the adult AML service.
- 6.1.4 Able to speak and read English.
- 6.1.5 Willing and able to provide informed consent.

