11.0 STATISTICAL CONSIDERATIONS

11.1 Introduction and sample size

To improve the strength of the findings as well as reporting of these findings, we will follow the recommendations of STROBE Statement (see study document ‘STROBE Criteria’) which provides guidelines of how to discuss and report study design, analysis, and findings in manuscript writing.

There is no targeted number for enrollment on this study. Instead, we plan to enroll all eligible patients continuously for duration of 36-40 months from study activation. We anticipate enrolling approximately 1000 patients from all sites but we will allow enrollment of more patients if enrollment rates were unexpectedly higher.

Based on a preliminary screen of the SCCA records over years 2008-2009, approximately 180, 125, 120, and 75 eligible patients with AML were seen annually at the 4 collaborating institutions, respectively, for an annual total of 500 patients. We anticipate enrollment rate of approximately ~65% resulting in a total of approximately 1000 patients observed over 3 years. Based on a preliminary screen, we anticipate that 50% (n=500) will be ≥60 years of age. Among the remaining 500 younger patients, we would anticipate (based on historical distribution of comorbidity scores among HCT recipients) that approximately 35% (n = 170) will have significant comorbidities (scores of ≥3). This suggests that the combined cohort of older or medically infirm patients eligible for studying the rate of receiving allogeneic HCT will be approximately 670 patients over 3 years. **Table 2** shows an estimate of the minimal increment in incidence of HCT detectable with 80% power at the 2-sided 0.05 level of significance, for varying assumptions about the prevalence of the risk factor. These estimates assume a time-to-event analysis, 25% overall incidence at 2 years post-initial therapy and 25% incidence of death without HCT as a competing risk.

Prevalence of risk factor or group	Increment in HCT incidence (HR)
10%	0.17 (1.9)
20%	0.13 (1.7)
30%	0.11 (1.6)
40%	0.10 (1.6)

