(1) Older and medically infirm patients who were prospectively enrolled for 2-years under SA2 and who completed initial intensive therapy will then represent a cohort of patients eligible to receive allogeneic HCT or additional conventional therapy ($n=670$). Based on preliminary screen of databases of collaborating centers, we estimate that approximately 25% of the 670 patients will undergo HCT within the time frame of the study. Patients who do or do not undergo HCT will be compared for NRM, OS, DFS, toxicities, QOL, function, utilization and satisfaction with care. Survivors at 3, 6, and 9 months will be compared for these two outcomes.

(2) Primary Outcomes: (i) Proportional hazards regression models for the sub-distributions of competing risks[111] will be used to evaluate impact of HCT and other factors on time-to-event outcomes (NRM, OS, and DFS). Since HCT may be received well after completion of induction and consolidation therapy, it will be analyzed as a time-dependent covariate,[110]so that the comparison is based on patients who have survived for comparable lengths of time. Similarly, patients who are not newly diagnosed at enrollment will be handled via left truncation – i.e., they will enter the set of patients at risk based on time since diagnosis. This analysis will be adjusted for the risk-stratification model, including comorbidities, disease response, age, and other variables; pre-exposure QOL scores; socio-demographic variables, including driving time to treating centers, income, marital status, and other variables; ranks of patient and physician surveys of decision-making style and treatment values; and the institution where the patient was treated. The evaluation of HCT as a risk factor may be complicated by the likely non-proportionality of hazards. In the short-term interval after HCT the risk of death may increase relative to those alive but not transplanted, then decline due to decreased relapse. We will assess this possibility by allowing the hazard ratio for HCT to vary by time after transplant in a time-dependent manner. All P values will be based on likelihood ratio statistics and will be 2-sided. Multivariate P values for a variable will reflect adjustment for all other variables in the model. Measures of precision for the HR or risk differences will be provided in form of confidence intervals.

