(ii) Landmark analyses for all patients alive at 3, 6, and 9 months post-induction, based on prior history of HCT, will be used to partially compensate for the time-dependent nature of the intervention and early death. A possible approach to describe the effect of HCT on outcome will be to divide the time axis into short intervals (for example, 3-6 months) and to estimate the actual hazard of the event of interest during the interval in 3 different states: not transplanted, early after transplant, late after transplant. This will be based on a simple

Protocol 2368.00

exponential assumption: i.e., the number of events in each state divided by the number of person-years at risk in each state. These hazard rates would yield estimates of OS probabilities, which could then be combined to yield estimates of OS probability over longer intervals, for example 1 or 2 years. The usefulness of such estimates would depend on relative stability of the hazard rates as a function of time since initial therapy.

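### For NRM, the named subdistribution model keeps relapsed and dead patients at risk, against the plan's own aim; the error's size and direction depend on an unstated coding of HCT after relapse (for OS and DFS only the name is wrong)

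*Combined protocol and SAP*

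**What the plan says.** Section 11.3(2)(i) names a single model for all three primary outcomes: "Proportional hazards regression models for the sub-distributions of competing risks[111] will be used to evaluate impact of HCT", where the outcomes are listed as "impact of HCT and other factors on time-to-event outcomes (NRM, OS, and DFS". Reference 111 is the subdistribution (Fine-Gray) paper. HCT enters as a time-dependent covariate, "so that the comparison is based on patients who have survived for comparable lengths of time". Two further features are added:

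- "patients who are not newly diagnosed at enrollment will be handled via left truncation".
- For non-proportional hazards: "We will assess this possibility by allowing the hazard ratio for HCT to vary by time after transplant in a time-dependent manner".

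Section 6.1.2 adds: "Patients with primary refractory or first relapse presenting for salvage chemotherapy will be allowed". Section 11.3(2)(ii), also under Primary Outcomes, adds "Landmark analyses for all patients alive at 3, 6, and 9 months post-induction".

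The plan does not define NRM's competing event. It does not say how HCT status is carried after that event, or what the event is for patients who enter already refractory or relapsed. No cause-specific model for NRM is named. Section 11.2(5), by contrast, names Cox regression for the incidence of HCT, so the authors do use the two terms separately.

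**The concern.** A subdistribution risk set keeps everyone who has had the competing event until the end of follow-up. For NRM that means relapsed patients, including those who have since died. They cannot have the event, yet they count in the denominator. Their time since transplant has no natural meaning after death, although the HCT effect is to vary with it. Comparison among patients who have survived equally long, and left truncation on time since diagnosis, both describe ordinary risk sets.

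NRM is one of the outcomes in primary objective 5.1.2.1, and section 4.0 says the data should help individualize treatment recommendations. An apparent effect of HCT on NRM that comes only from the risk-set definition would bear directly on that use.

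**Working it through.** **The plan's own figure.** No NRM hazard ratio or NRM power is stated. The only power figure for this comparison (11.1) is at least 80% for a 13-point OS gain, 170 HCT versus 505 non-HCT, two-sided 0.05. At the least favourable non-HCT OS, 43.5%:
- pooled p = (505×0.435 + 170×0.565)/675 = 0.468
- null SE = √[0.468×0.532×(1/505 + 1/170)] = 0.0442; alternative SE = √[0.435×0.565×(1/505 + 1/170)] = 0.0440
- power = Φ[(0.13 − 1.96×0.0442)/0.0440] = Φ(0.98) = 0.84

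The figure reproduces. It concerns OS and is not affected by this point.

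**Inputs for NRM.** From 11.1: "25% overall incidence at 2 years post-initial therapy and 25% incidence of death without HCT as a competing risk". These rates were given for Table 2, the analysis of receiving HCT; 11.3(1) also uses 25% HCT. From 11.3 and 4.0: 670 patients, 24 months. Assumed: constant hazards, relapse incidence, survival after relapse, HCT after relapse.

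**Mechanism.** Let NRM, relapse and HCT hazards be a, r and g, with HCT changing nothing and HCT status frozen at relapse. At time t, as shares of all patients:
- event-free, no HCT: e^−(a+r+g)t
- event-free, HCT: e^−(a+r)t − e^−(a+r+g)t
- relapsed, no HCT: r/(a+r+g) × [1 − e^−(a+r+g)t]
- relapsed, HCT: r/(a+r) × [1 − e^−(a+r)t] minus the line above

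NRM occurs only in the first two groups; the Fine-Gray risk set holds all four. Take a = 0.091, r = 0.127, g = 0.181 per year. Over 2 years HCT is 0.181/0.399 × (1 − e^−0.798) = 25%, relapse is 0.127/0.218 × (1 − e^−0.436) = 21% and NRM is 0.091/0.218 × (1 − e^−0.436) = 15%. With an assumed 6-month median survival after relapse, death without HCT is 25%.

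At month 12:
- event-free: 0.671 without HCT, 0.133 with HCT
- relapsed: 0.105 without HCT, 0.009 with HCT
- odds of HCT among NRM events: 0.133/0.671 = 0.198
- odds of HCT in the risk set: 0.1425/0.7757 = 0.184
- apparent hazard ratio at that time: 0.198/0.184 = 1.08

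Patients who cannot have the event make up 0.1047/0.7757 = 13% of the no-HCT risk set but 0.0094/0.1425 = 7% of the HCT risk set, because relapses came earlier, when fewer patients had been transplanted. Over 24 months the partial-likelihood solution is 1.10-1.11.

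**Null NRM hazard ratio at 25% HCT and 25% death without HCT**

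| Assumed relapse at 2 years | Frozen at relapse | Updated, equal HCT hazard |
|---|---|---|
| 10% | 1.05 | 1.01-1.03 |
| 20% | 1.10-1.11 | 1.03-1.06 |
| 30% | 1.14-1.16 | 1.04-1.08 |
| 40% | 1.20-1.22 | 1.05-1.08 |

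Median survival after relapse is 3-12 months (6-12 at 40%). The cause-specific Cox model gives about 1.00 throughout. Other cases:
- Splitting the 25% deaths directly into NRM and relapse death, with relapse death as the competing event: 1.03-1.11 frozen, 1.07 at an even split.
- Widest frozen value: 1.25, at about 46% relapse and 12-month median survival after relapse.
- Status updated with twice the HCT hazard after relapse: about 0.92-1.02; for example 0.93 at 40% relapse and 12-month survival.

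**At 670 patients.** Rejection at the 5% level under frozen status is about 5-9%, against 4-6% for cause-specific Cox. The shift in log hazard ratio (ln 1.05 = 0.05 to ln 1.22 = 0.20) is small beside a standard error of about 0.24-0.40.

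**Landmarks.** Fine-Gray from 3, 6 and 9 months with HCT status fixed (relapse 20% and 40%) gives 1.00-1.10 among all patients alive, and 1.00-1.02 among those alive and relapse-free.

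**OS and DFS.** With no competing event the two risk sets coincide. Fine-Gray and Cox estimates for simulated DFS differed by 0.0; OS follows by the same identity.

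**The case against.** **A loose label.** Time-dependent HCT, left truncation and the stated aim all describe ordinary risk sets, so the authors may have meant Cox. That is plausible, but reference 111 is specific and an analyst following the text would fit the subdistribution model. On this reading the remedy is still the same edit.

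**Size and direction are not fixed by the plan.** This stands. A reader might infer that the plan's own rates give a hazard ratio of 1.1-1.2 towards harm. They do not: 11.1 gives neither a relapse rate nor a split of deaths for this cohort, and nothing says HCT status is frozen at relapse. For living relapsed patients later HCT is observed, since treatment details are collected at every time point after enrollment (8.1.9.1). With updating, the ratio can fall on either side of 1. What remains is that status after death is undefined under either coding, and that the plan does not choose between them.

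**Larger figures.** Rates from the all-HCT cohort in 3.3 (relapse 41%, NRM 27%), if reached by 2 years, give 1.29-1.31 frozen and 20-26% rejection. They imply 46-48% death without HCT, well above 25%, so they should not be carried over to this study.

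**Landmarks already planned.** They are listed under Primary Outcomes and should not be dismissed as supplementary. They do reduce the problem. The plan itself claims only partial compensation from them, and they leave the regression in (i) unchanged.

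**Conclusion.** The concern holds for the NRM regression. The named model contradicts the stated aim, and the competing event and the coding of HCT after it are unspecified. With no true effect, the NRM hazard ratio is about 1.03-1.25 under frozen status and about 0.92-1.08 with updating at an equal or doubled HCT hazard. This rests on relapse as the competing event, constant hazards, assumed relapse of about 10-40% (about 7-46% at the outer limits of the frozen range) and assumed survival after relapse. False significance is only slightly raised, about 5-9%. A reader might infer that OS and DFS are biased as well; they are not, and only the model's name needs correcting there. The change is worth making before analysis because NRM is a primary outcome and the estimate otherwise turns on an unstated choice.

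**What to change.** - Name Cox models for OS and DFS.
- For NRM, name the competing event. Use cause-specific Cox models for NRM and for relapse or progression, reported together, with the planned time-dependent HCT, time-varying HCT effect and left truncation.
- Define the competing event for patients enrolled refractory or in first relapse (for example, progression, persistent disease or a further relapse after entry), and stratify by entry status in addition to the planned disease-response adjustment. With an assumed 10-30% of such entrants and assumed higher event hazards, the cause-specific null hazard ratio was 0.99-1.02 when stratified and 0.86-0.99 when not.
- Limit cumulative-incidence or Fine-Gray estimates of the HCT effect to the planned landmarks, among patients alive and free of the competing event, with HCT status fixed at the landmark.

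The cost is text in 11.3(2)(i) and (ii). The software is standard, and disease status is already collected (8.1.13.3). The downside is that a cause-specific hazard ratio does not by itself give cumulative incidence, so landmark incidence curves should be shown beside it.

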(iii) Given the expected bias in treatment selection and to further enhance our ability of obtaining accurate statistical inferences, we will use propensity scores. Propensity scores will estimate the probability on the basis of all patients and center characteristics that patients would proceed to allogeneic HCT with the use of proportional hazard model to adjust for between-group differences in the previously mentioned characteristics.[112] The magnitude of divergence of propensity scores between the two approaches will allow us to assess the amount of bias in treatment selection. Inverse-probability-weighting based on the propensity score will then be used as a secondary tool to adjust for differences between the two treatment-groups [113]. This approach will be implemented to create balance and it involves weighting each patient who received HCT by the inverse of the probability that he or she would be selected for HCT and weighting each patient who received conventional treatment by the inverse of the probability that he or she would be selected for conventional treatment. We will verify the performance of the propensity model by comparing the distribution of covariates and propensity scores between treatment groups both before and after inverse probability weighting.[114] Adjusted OS curves will be estimated using the inverse-probability-weighting approach of Cole and Hernan.[115] Assessment of benefit of either approach will be done in quintiles of propensity scores.

(iv) Sensitivity analyses will be performed to better understand any statistical disagreement between the models. First, OS curves for comparing both groups will be estimated using a double robust strategy of combining the inverse-probability weighting with the regression-based estimation [116]. Secondly, propensity scores will be used to construct matched samples from both groups to be used for simple matched pair analyses which adjust for confounding variables. Finally, we will use the method of Lin et al [117] to assess whether the observed differences in the rate of death could be due to an unmeasured confounder.

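### Section 11.3(2)(iii)-(iv) groups patients by the treatment they eventually received, with no time alignment, so from a shared start before HCT the propensity-based OS analyses favour HCT

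*Combined protocol and SAP*

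**What the plan says.** Section 11.3(2) has four layers.

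- Item (i), the primary model: "Since HCT may be received well after completion of induction and consolidation therapy, it will be analyzed as a time-dependent covariate". The stated aim is to compare patients who have survived equally long.
- Item (ii): "Landmark analyses for all patients alive at 3, 6, and 9 months post-induction, based on prior history of HCT".
- Item (iii): a proportional hazards model gives the propensity to proceed to HCT. Then "Inverse-probability-weighting based on the propensity score will then be used as a secondary tool to adjust for differences between the two treatment-groups". Each patient gets one weight according to the treatment received: "weighting each patient who received HCT by the inverse of the probability that he or she would be selected for HCT", with the mirror-image weight for conventional treatment. Adjusted OS curves follow, and "Assessment of benefit of either approach will be done in quintiles of propensity scores".
- Item (iv), sensitivity analyses: "OS curves for comparing both groups will be estimated using a double robust strategy", and "propensity scores will be used to construct matched samples from both groups to be used for simple matched pair analyses".

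Section 11.3(1) adds that "Survivors at 3, 6, and 9 months will be compared for these two outcomes", without linking this to the propensity analyses. Items (iii) and (iv) name no time origin, landmark, time-varying weight or matching on time survived.

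**The concern.** A patient enters the HCT group in (iii)-(iv) only by living long enough to be transplanted. If follow-up of both groups starts at diagnosis, enrollment or end of induction, recipients cannot die during the wait, while everyone who dies waiting is counted as conventionally treated. This is an error in allocating person-time. Weighting, stratifying or matching on baseline covariates does not correct it.

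These analyses are meant to support the primary model, and item (iv) is there to explain disagreement between models. With this grouping they could lend false support to HCT in older and infirm patients. They could also create a disagreement with the time-dependent model that reflects only how the groups were formed.

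**Working it through.** **The plan's own figure.** Section 11.1 gives at least 80% power for a 13-point OS difference with 170 versus 505 patients, two-sided 0.05, leaving time-dependence aside. No baseline OS is given. Power is lowest at a non-HCT OS of about 45%:

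- pooled proportion = (505×0.45 + 170×0.58)/675 = 0.483
- null SE = √[0.483×0.517×(1/505 + 1/170)] = 0.0443
- alternative SE = √[0.45×0.55/505 + 0.58×0.42/170] = 0.0439
- power = Φ[(0.13 − 1.96×0.0443)/0.0439] = Φ(0.98) ≈ 84%

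The statement is reproduced. It does not address the grouping in (iii)-(iv).

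**Inputs for the bias.**
- 25% transplanted: Sections 11.1 and 11.3(1).
- 25% death without HCT at 2 years: Section 11.1, borrowed from the Table 2 power assumptions.
- Timing: Section 8.0 sets 3, 6, 12 and 18 months after HCT roughly against 9, 12, 18 and 24 months from enrollment. Each pair differs by 6 months, so the schedule implies HCT near month 6. The distribution around that is not given.
- Assumed: HCT has no effect on death; death hazard *m* is constant; HCT hazard *h* is constant within a window from month *a* to month *b*; both groups are followed from the same origin.

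**Formulas** (24-month horizon).
- OS = e^(−24m), the same for everyone
- P = P(HCT) = e^(−ma) × h/(m+h) × [1 − e^(−(m+h)(b−a))]
- A = P(HCT and alive at 24 months) = OS × [1 − e^(−h(b−a))]
- death without HCT = (1 − OS) − (P − A)
- spurious gain = A/P − (OS − A)/(1 − P)

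**Worked case, window months 3-9.** Solving for P = 0.25 and 25% death without HCT gives m = 0.01556 and h = 0.05329 per month.
- P = 0.9544 × 0.7740 × 0.3384 = 0.250
- OS = e^(−0.3734) = 0.688
- A = 0.6884 × 0.2737 = 0.188
- death without HCT = 0.3116 − 0.0616 = 0.250
- recipients 0.1884/0.25 = 75.4%; others 0.5000/0.75 = 66.7%; gain 8.7 points, with no treatment effect

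**All windows.** The last two columns solve for P = 0.25 at an assumed OS of 35% instead.

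| HCT window (months) | 2-year OS, recipients / others | Gain, 25% death without HCT | Gain, OS 35% | Death without HCT implied by OS 35% |
|---|---|---|---|---|
| 0-3 | 68.8 / 66.7% | 2.1 | 3.0 | 49% |
| 3-6 | 73.3 / 66.7% | 6.6 | 9.9 | 51% |
| 4-8 | 75.5 / 66.7% | 8.8 | 13.6 | 51% |
| 5-7 | 75.6 / 66.7% | 8.9 | 13.8 | 51% |
| 3-9 | 75.4 / 66.7% | 8.7 | 13.3 | 51% |
| 0-24 | 82.8 / 66.7% | 16.2 | 25.6 | 54% |

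**Do the planned methods remove it?** A simulation used 500 cohorts of 670, no HCT effect, a proportional hazards propensity and one fully measured baseline confounder (assumed log HR per SD +0.4 for death, −0.4 for HCT). With 25% death without HCT and window 3-9, the spurious gains were: weighting 8.5, quintiles 8.8, doubly robust 8.3, matched pairs 7.9 points (Monte Carlo SE at most 0.25). All four stay close to the closed-form 8.7.

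**Do (i) and (ii) avoid it?** A separate null simulation spread HCT over 24 months and used a logistic propensity. Weighting gave a false 16.3 points. On the same data the time-dependent exposure ratio was 1.01 and the 6-month landmark ratio 1.02.

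**The case against.** The best counter-reading is that (iii)-(iv) are only a confounding-adjustment layer on (i)-(ii). All four items share one heading, Section 11.1 recognises that the treatment groups are time-dependent, 11.3(1) announces survivor comparisons, and the propensity comes from a proportional hazards model, which could support time-varying weights. On that reading a sentence or two of clarification is enough.

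The text does not say this. Item (iii) is introduced to deal with treatment selection and refers back only to covariates. A hazards model for uptake does not reassign survival time before HCT, and the weights are described per patient by treatment received. Simple matched pairs inherit nothing from a separate time-dependent model.

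Three parts of the objection stand:

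- The direction depends on a shared origin before HCT. Section 11.3(1) requires completed initial therapy for cohort entry and (ii) counts from induction, but (iii)-(iv) adopt neither as time zero. Counting recipients from HCT instead would misalign the groups in another way.
- The schedule does suggest when HCT is expected, so windows around month 6 are the natural reference.
- The 16- and 26-point figures need HCT at a constant rate over all 24 months, which the schedule does not suggest. The 26 also needs about 54% death without HCT, against the plan's 25%. They are outer bounds.

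**Conclusion.** The concern holds for the secondary analyses in 11.3(2)(iii) and the doubly robust and matched-pair analyses in (iv). Followed as written from a common origin before HCT, they are biased toward HCT even with every baseline confounder measured. For HCT around month 6 the illustrative size is about 7 to 9 points of 2-year OS on the plan's 25% death without HCT, and about 10 to 14 points at an assumed OS of 35%. HCT all by month 3 would reduce it to about 2 to 3 points. These figures rest on constant hazards, no HCT effect and 25% transplanted. The documents give neither the distribution of HCT times nor the cohort's OS.

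A reader might infer that the plan's main HCT comparison is compromised. It is not: (i) treats HCT as time-dependent and (ii) uses landmarks, and neither carries this bias. Nor do the documents support a claim that the bias generally exceeds the 13-point difference in the power statement. With HCT near month 6 it does so only under much heavier mortality than the plan assumes.

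**What to change.** State in 11.3(2)(iii)-(iv) that no propensity-based analysis groups patients by HCT received at a later time. Then:

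- **Weighting, quintiles and doubly robust curves:** either run them within the planned 3-, 6- and 9-month landmark sets, with HCT status at the landmark, follow-up from the landmark, and pre-HCT covariate values for those already transplanted; or use time-varying weights in which HCT switches on at day 0.
- **Matched pairs:** match each recipient at day 0 to a patient alive and not yet transplanted at the same time since diagnosis, using covariates known by then.

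If the authors already intend such alignment, stating it settles the point.

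The pre-HCT restriction matters. In a null simulation where HCT was assumed to lower a covariate by 1 SD without affecting death, 6-month landmark weighting with post-HCT values was biased by +3.9 to +6.3 points across three scenarios. With the last pre-HCT values the bias was −0.2 to −0.8. Day-0 matching gave 0.0 to −0.3 points, and time-varying weights gave HR 0.99.

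The cost is SAP wording, moderate programming and some precision; no new data are needed. Deaths before each landmark are excluded from it. Early landmarks hold few recipients: of 670 patients on the plan's 25%/25%, those transplanted and alive at 3, 6 and 9 months number about 0, 90 and 159 for window 3-9, and 27, 51 and 72 if HCT is spread over 24 months. The SAP must also state the carry-forward assumption, since recipients' values predate HCT while comparators' run up to the landmark.
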